Data will be summarized by group and in total. In summary tables of continuous variables, the minimum, maximum, mean, and standard deviation will be presented with one decimal place. We will use counts and percentages in table for categorical variables. The denominator for each percentage will be the number of participants within the group unless otherwise specified. All hypothesis testing will be carried out at a two-tailed Type I error rate of $\alpha = .05$ unless otherwise specified. P-values will be rounded to three decimal places with a minimum of < 0.001 in tables. If statistical methods change during analysis, this will be documented in all reports with justification. Additional analyses of these data will be inevitable, but any exploratory analyses will be clearly marked as such.

Statistical power analysis and sample size selection

IRT and DIF analyses require large samples due to the large number of free parameters to be estimated. The proposed sample size herein is larger than other successful implementations of these same analyses carried out in other IRT studies.¹⁶⁻¹⁹ Moreover, we have carried out computer simulations to determine if our proposed sample sizes will be sufficient to create IRT models. We assumed a one-factor model across two groups at $n = 100$ each with standardized factor loadings set to .7 for eight questionnaire items. We used two groups for this simulation to ensure that any pairwise model comparisons would have adequate power. For this simulation, we specified that a non-significant model χ^2 was a good fit, which is a conservative decision because this particular test is highly sensitive relative to other measures of model fit, especially with large samples. Across 500 iterations, a good-fitting model was identified across groups 90% of the time. Even dropping the sample size to as low as $n = 50$ would identify a good-fitting model 84% of the time.

Missing data

We will describe the rate of missing data on an item-by-item basis using frequency tables in R. We do not anticipate high rates of missing data, but we will conduct subgroup analyses by health literacy, site, and administration mode as need to help diagnose any problems with missing data. For DIF analyses, IRT models

Table 1	
Visit 1 (Baseline)	Description of instrument
Language Assessment	To determine testing in English or Spanish
Single Item Health Literacy Screener	To screen for possible literacy status

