Each participant will be asked to complete a baseline assessment (Visit 1), three-month follow-up (Visit 2), and a six-month follow-up (Visit 3). Longitudinal data will be analyzed, within language and within mode of administration (paper-based vs. talking touchscreen), on a scale-by-scale basis using multiple-group factor analysis to compare in Mplus software (see Table 3 schematic below). All items will be treated as categorical indicators with response categories collapsed if there are fewer than five responses for a given response option.

Table 3: Schematic of multiple-group confirmatory factor analysis to be used on a scale-by-scale basis			
	Visit 1	Visit 2	Visit 3
Adequate health literacy	Factor loadings/ IRT parameters	Factor loadings/ IRT parameters	Factor loadings/ IRT parameters
Low health literacy	Factor loadings/ IRT parameters	Factor loadings/ IRT parameters	Factor loadings/ IRT parameters

We hypothesize that a metric invariable model will fit well for the talking touchscreen method. Acceptable fit will be defined as $CFI \geq .90$, $TLI \geq .90$, and $RMSEA \leq .10$. We hypothesize that unacceptable fit indices will be obtained for the paper-based testing. For descriptive statistics, we will report all fit indices produced by Mplus as well as factor loadings for each item. Longitudinal data will also be used to develop new longitudinal DIF tools in R, but these results will be considered exploratory until they can be tried and tested in other data sets.

Study Populations

The study population includes medical patients and community member, all might which complete questionnaires in other clinical and research contexts, ages 18 and older.

Study Variables

Demographics

All demographic variables are described in the protocol. We will report descriptive statistics of all demographics within language group as well as in total. We do not have specific hypotheses about demographics, but may conduct and report analyses of them, as well as presented additional analyses of demographics based on requests from manuscript reviewers.

Health literacy and numeracy

HealthLiTT and the NUMI will be used to determine health literacy groups using the above-described cutoffs. HealthLiTT is our main health literacy variable. All analyses of the NUMI are secondary.

Health questionnaires

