The following questionnaires will be subjected to DIF analyses: the PROMIS Profile (physical function, anxiety, depression, fatigue, sleep disturbance, ability to participate in social roles and activities, and pain interference), the Berlin Questionnaire (for sleep), the NIH Toolbox scale for purpose and meaning, the PTSD checklist (20 symptom items assessing overall PTSD symptoms), the Ruminative Responses Scale (total score and brooding and reflection subscales), and the PHQ-9.

Screening tools for Alzheimer's disease and related dementias (ADRD)

Based on supplemental funding, a brief battery of screening tools for ADRD was added to the project. These screening tools include the Montreal Cognitive Assessment Test-Basic (MOCA-B),²⁰ the Visuospatial/Executive, Attention, and Language subtests of the MOCA 8.1,²¹ and the Body Orientation, Fist/Palm, Judgement, and Language Generativity – Animal Naming subtests of the Rowland universal dementia assessment scale.²² The first participant completed the ADRD screening tools on 10 July 2019. These tools are given at the baseline visit, but if the baseline visit has already occurred, the tools are given at one of the follow-up visits (Visit 2 or Visit 3).

Interim analyses to ensure data quality

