We hypothesize that DIF will be observed across adequate versus low levels of health literacy as measured by HealthLiTT.¹⁵ This hypothesis was formulated before any data were examined. In terms of direction, we predict that low-health-literacy groups will show lower item slopes. All questionnaires and subscales mentioned in the “Core battery for DIF Testing” section of protocol will undergo DIF testing. To examine DIF across health literacy status, we will conduct separate analyses within language and within testing format (paper-based vs. talking touchscreen). The overall N for these analyses, within strata, will be 304. We will use the *lordif* package in R for these analyses. This involves several steps. Four models are fit to the data (see Box 1). The models are regressions that link the probability of response type (e.g., “never”, “rarely”, “sometimes”, “often”, “always”) to a latent trait. If an item is free of DIF, then group (e.g., adequate vs. low health literacy) should have no effect. Thus, Model 2 and Model 3 should not fit significantly better than Model 1. It is well known that statistical significance is influenced, in part, by sample size. Thus, *lordif* uses effect-size measures to detect DIF, and to flag individual items where the effect of group exceeds a particular threshold. Effect sizes indicative of DIF will be chosen for each scale based on a Monte Carlo simulation carried out in *lordif*, which returns an effect size that would be unlikely given the null hypothesis of no DIF.

The following *a priori* decisions are important. We will use a Type I error rate of $\alpha = .01$ to generate the McFadden ΔR^2 effect size for each item that would be considered unusual if the null hypothesis of no DIF were true. Within each scale, we will select the smallest McFadden R^2 across all of the items. The minimum effect size we will consider

Box 1: Models fit by lordif

Model 0: $\text{logit}[P(Y \geq k)] = \alpha_k$
Model 1: $\text{logit}[P(Y \geq k)] = \alpha_k + \beta_1 (\text{ability})$
Model 2: $\text{logit}[P(Y \geq k)] = \alpha_k + \beta_1 (\text{ability}) + \beta_2 (\text{group})$
Model 3: $\text{logit}[P(Y \geq k)] = \alpha_k + \beta_1 (\text{ability}) + \beta_2 (\text{group}) + \beta_3 (\text{ability} \times \text{group})$

Note: α and β are logistic regression parameters. k refers to the number of thresholds needed for each item.

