We will determine the degree to which health literacy moderates the relationship between depression and associated constructs of rumination, pain intensity, pain interference, sleep disturbance, and fatigue. Depression will be measured using both the Patient Health Questionnaire (PHQ-9), a nine-item scale with each item scored between 0 and 3 providing a 0-27 severity score with higher scores representing greater depression severity. The NIH Patient-Reported Outcomes Measurement Information System (PROMIS Profile 57 v 2.0) will also be used to measure depression, as well as pain intensity, pain interference, sleep disturbance, and fatigue. PROMIS is a self-report measure with subscales producing a T-Score; higher T-scores representing a higher level of the construct. Rumination will be measured using the Ruminative Responses Scale (RRS) short form, a 10-item form that measures two factors, brooding and reflection. The RRS uses a four-point scale for each item with a total score derived from the sum of the individual items. Higher scores indicate higher levels of rumination. All variables will be examined in a continuous manner, rather than using cut scores.

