(dependent variables) on brooding, reflection, depression, and the two product terms (depression \times brooding, depression \times reflection); depression will be the moderator. The statistical significance of these two product terms will be evaluated at .05 and effect sizes will be reported. We will then conduct addition moderation analyses with age, gender, and language in the same fashion as described above. Depending on the results, moderation will be summarized using simple-slope analyses and visualization.

Other Approaches (Exploratory)

We will explore these associations in other software (e.g., lavaan, mirt)^{59, 60} for consistency across software. Supplementary results will be made available in an open-science repository.

Backup plan for factor analyses. If we have difficulty identifying latent variable models, we will reframe the analyses of cognition around general levels of cognition using the MoCA-B total score.

Factor analysis of the Ruminative Responses Scale (RRS);

Added 26 January 2023

Although the RRS is commonly organized into two factors – brooding and reflection – some literature has failed to support this two-factor structure.⁶¹ To clarify the structure of the RRS, we will randomly divide our baseline sample into an exploratory and confirmatory half, and then conduct exploratory and confirmatory factor analyses. To determine the number of factors, we will use primarily parallel analysis as implemented in the *psych* package, specifying that the items are ordered categories. Secondarily, we will also examine parallel analysis as implemented in the *nFactors* package and the method of Lubbe (2019).⁵⁶

Based on previous literature, we anticipate that a one- or two-factor model will be a good fit to the RRS, but we will be guided by parallel analysis. Although factor loadings are continuous, we will flag any factor loading greater than or equal to 0.3 as an indicator of the factor. For the factor analyses, we will use the *mirt* package using a graded response model for ordered categories. We will explore different factor rotations, although we anticipate that an oblique solution will be most appropriate, such as the *geominQ* rotation that allows for factors to be correlated.

For validity of any factor solutions, we will correlate the RRS factors with depression (i.e., PROMIS Depression and PHQ-9) and expect statistically significant associations.

Other Interim and Exploratory Analyses

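### Longitudinal metric invariance is judged only by the absolute fit of the equal-loadings model, which can pass unequal loadings and fail equal ones

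*SAP*

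**What the plan says.** SAP, Study Timepoints, plans a multiple-group confirmatory factor analysis for each scale, run separately within language and administration mode. Table 3 lays it out as two literacy groups by three visits. On the items: "All items will be treated as categorical indicators with response categories collapsed" where a response option is sparse.

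The decision rule is: "We hypothesize that a metric invariable model will fit well for the talking touchscreen method. Acceptable fit will be defined as" CFI and TLI of at least .90 with RMSEA of at most .10. For the other mode: "We hypothesize that unacceptable fit indices will be obtained for the paper-based testing". Fit indices and item loadings are otherwise reported descriptively, and new longitudinal DIF tools are labelled exploratory.

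The section names no configural (unconstrained) model, difference test, change-in-fit limit or joint model of the two modes. It does not say how one person's three visits are linked, or how item scales and thresholds are set.

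**The concern.** Evidence on metric invariance is the deterioration in fit when loadings are constrained equal. Absolute fit of the constrained model combines that deterioration with how well the assumed factor structure fits at all. The verdict therefore depends on dimensionality, loading strength and how repeated visits are modelled, as well as on equality of loadings.

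Two errors follow. A pass for touchscreen need not mean equal loadings, and a failure for paper need not mean unequal ones. Comparing an acceptable label in one mode with an unacceptable label in the other is also not a test that the modes differ. This is the stated hypothesis about whether touchscreen preserves measurement over the three visits, so the trial could report it as supported or refuted for reasons unrelated to literacy or mode.

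**Working it through.** **1. The SAP's own simulation.** Statistical power analysis and sample size selection assumes one factor, two groups and "standardized factor loadings set to .7 for eight questionnaire items". It reports a non-significant model chi-square in 90% of runs at n = 100 per group and 84% at n = 50. A two-group maximum-likelihood (ML) metric model reproduces this: 91.7% and 84.7% (1,000 runs). The simulation shows how often a correct model is accepted. It uses a different criterion from Study Timepoints and never examines unequal loadings.

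**2. ML check, two groups.** Keep those values and cut four of the eight low-literacy loadings from .7 to .35.
- Metric df: 2 × 36 − (8 loadings + 1 factor variance + 16 residuals) = 47. Baseline df: 2 × 28 = 56. Configural df: 72 − 32 = 40.
- Baseline discrepancy, the mean of −ln det R over the groups: (3.225 + 1.529)/2 = 2.377. Minimised metric discrepancy: F = .0949. The configural model fits exactly.
- CFI = 1 − .0949/2.377 = **.960**.
- TLI = 1 − (.0949/47)/(2.377/56) = **.952**.
- RMSEA = √(2 × .0949/47) = **.064**.

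All three limits are met. The nested test on 47 − 40 = 7 df at 304 persons (152 per group) has noncentrality 304 × .0949 = 28.8 and power .99. With six independent literacy-by-visit cells, ML gives .960/.957/.061.

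**3. Categorical items over three visits, as planned.** These are population values with a mean-and-variance-adjusted weighted least squares fit. Assumptions: item scales fixed, five categories (symmetric or skewed), factor correlation across visits .5-.9, same-item residual correlation 0-.4. Drift over correlated visits used .7 and .2.

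| Low-literacy loadings on four items | Layout | CFI | TLI | RMSEA | Rule |
|---|---|---|---|---|---|
| .35 at every visit | six cells | .947-.948 | .943 | .079-.091 | pass |
| .35 at every visit | correlated visits | .930-.945 | .920-.937 | .048-.071 | pass |
| .7, .525, .35 at visits 1, 2, 3 | both | .965-.977 | .960-.975 | .042-.065 | pass |

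Configural CFI is 1.000, so the constraint costs .052-.070 when halving is constant and .023-.035 when it develops over visits. The rule ignores this cost.

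Approximate power of the nested test (155 − 120 = 35 df in the six-cell layout), alpha .05:
- For the planned stratum ("The overall N for these analyses, within strata, will be 304"): 1.00 (constant) and .98-1.00 (drift).
- With 728/4 = 182 per stratum (equal split, no dropout assumed): .98-1.00 and .79-.93.

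**4. Sampling runs, constant halving, ML, 152 per group.** The SAP rule passes the data 97% of the time (two groups) and 100% (three visits). The nested test rejects 98% and 100%, against 6% and 5% when loadings are invariant (three-visit results from 40 runs).

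**5. The converse.** Health questionnaires lists "the Ruminative Responses Scale (total score and brooding and reflection subscales" for DIF analysis. The depression-prediction section calls the form "a 10-item form that measures two factors, brooding and reflection", and the later RRS factor-analysis section notes that "some literature has failed to support this two-factor structure". Take ten four-category items with fully invariant loadings of .7-.8 on two factors, fitted as one factor per visit with correlated visits.
- Factor correlation .5-.6: CFI .819-.891, TLI .800-.880, a **fail**.
- Factor correlation .7: CFI .921-.937, a pass.

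In a simpler ML version, correlations of .5, .6 and .7 give CFI .734, .809 and .877. The configural model fits equally badly, so the failure says nothing about equality of loadings.

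**The case against.** **Coverage elsewhere.** Literacy differences in slope are already tested with nested models by lordif under Primary analyses, and constant halving is that kind of difference. This is fair for constant halving. lordif does not test loadings across visits, however, and the MNLFA uses baseline data from one scale in English speakers. The drift case is the longitudinal one, and the rule passes it too.

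**Assumptions.** Only the .7 and the eight items come from the SAP. The rule is also not blind: .8 against .4 on four items fails in six cells (RMSEA .120-.137), though it mostly passes with correlated visits (.070-.102), and cutting four loadings to .2 or lower fails in the two-group ML model. A single-visit categorical two-group model is borderline (RMSEA .089-.101). All this stands as a limit on size. The unstated parameterisation matters too: if all scale factors and thresholds were free across groups, equal loadings would not restrict the polychoric correlations. Metric and configural fit would then coincide, and the rule could detect no loading difference.

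**Randomised mode.** A structural fault shared by both arms should tend to pass or fail both, not give the predicted split. This tempers the consequence but does not remove it. For an invariant two-dimensional scale (correlation .5, skewed items, three visits), the rule passed 16% of runs at 152 per group and 28% at 100. With independent arms, touchscreen passing and paper failing then occurs by chance in .16 × .84 = 13% or .28 × .72 = 20% of scales. These rest on 25 runs each and are rough.

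**RRS.** Study Timepoints does not say the total is fitted as one factor. That is correct and should be stated.

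**Conclusion.** The concern holds. As written, the rule does not test metric invariance in either mode. At the SAP's simulation values it accepts a scale with half the low-literacy loadings halved, although the constraint costs .052-.070 in CFI and a nested test would almost always detect it at the planned stratum size. It can also reject a fully invariant scale that has two moderately correlated dimensions. The direction of error in a given arm cannot be predicted from the documents.

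The size depends on assumed thresholds, visit correlations, factor correlations and fixed item scales. The logical defect does not depend on them: no comparator is fitted and the modes are never compared directly. This should be corrected, but it concerns a secondary longitudinal analysis and does not affect the lordif results.

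**What to change.** Within each language and mode:

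1. Fit a configural model and use CFI, TLI and RMSEA only to judge whether it is adequate. This must come first: in the two-group ML runs the difference test over-rejected (9-18%) for an invariant scale when the one-factor baseline was wrong.
2. Fit the metric model across literacy groups and visits. Base the invariance decision on the nested comparison (DIFFTEST for categorical items) with a change-in-CFI limit fixed in advance.
3. Treat the visits as repeated measures, with correlated factors and same-item residual correlations. State the estimator, the parameterisation and the treatment of scale factors and thresholds.
4. State whether the RRS total is fitted as one factor.
5. Test directly whether literacy-related loading differences differ between paper and touchscreen.

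The cost is additional Mplus runs and SAP wording, with no new data. The smallest strata need care. If Spanish strata hold about (728 − 566)/2 = 81 people (assumed), nested power for constant halving falls to about .65-.80 with correlated visits. An ML difference test over-rejected at 17.5-22.5% with 50-100 per group over three visits (40 runs; not DIFFTEST). A short simulation of the chosen test's error rate at achieved sample sizes should accompany the change, especially for the 20-item PTSD checklist, which gives 60 indicators over three visits.

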read to them. We will analyze the talking touchscreen groups and paper-based groups separately. We hypothesize that the talking touchscreen will reduce health literacy-related test bias by level of health literacy, relative to traditional paper-based methods. This will be evidenced by fewer items being flagged for DIF in the group that receives the talking touchscreen. In terms of descriptive statistics to display the magnitude of effects, we will report effect sizes (McFadden's R^2) of DIF items, as well as test characteristic curves (TCCs) for DIF items. Among participants with low health literacy, we expect that the discrimination parameters of the touchscreen condition will be higher than the paper-based condition.

- **Determine the degree of differential item functioning (DIF) of tools relevant to clinical research across different levels of health literacy.** DIF analyses will be conducted to identify test bias by level of health literacy. This will ensure that individuals with low literacy are assessed fairly in clinical and research settings. We will assess a broadly applicable instrument to primary care – the PROMIS Profile, which measures anxiety, depression, fatigue, pain interference, pain intensity, physical function, sleep disturbance, and social roles and activities. Other questionnaires included in the study are shown in Table 1. We will stratify participants into low versus adequate literacy levels using Health LiTT (groups will be formed according to T scores of < 55 vs. 55+).¹⁵ A secondary analysis will use the NUMI, a measure of health numeracy, in three groups (low = 0-3, medium = 4-6, high = 7 or greater). Then, we will determine whether psychometric properties of each questionnaire scale are consistent for individuals with low health literacy versus adequate health literacy. We hypothesize that DIF will be observed for multiple scales using paper-and-pencil administration, suggesting a need to improve test items, and a need to examine alternative ways to administer these tools.

Statistical methodology

Overview

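### The SAP sets a no-DIF threshold for each item but no study-level criterion for its hypothesis that DIF will be observed, so chance flags alone can satisfy it

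*SAP*

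**What the plan says.** The prediction appears in three forms in the SAP.

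- Primary analyses, DIF by health literacy: "We hypothesize that DIF will be observed across adequate versus low levels of health literacy".
- Later in that section it is restated as an a priori hypothesis for paper-based testing. DIF is also expected on the touchscreen, but for fewer items and with smaller ΔR² values.
- Study Objectives: "We hypothesize that DIF will be observed for multiple scales using paper-and-pencil administration". The inference that items need improving is attached to this form.

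The scales are listed in Health questionnaires ("The following questionnaires will be subjected to DIF analyses"). For the strata, "we will conduct separate analyses within language and within testing format (paper-based vs. talking touchscreen"; the sample size is given as "The overall N for these analyses, within strata, will be 304".

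The flagging rule works item by item. A Monte Carlo step in *lordif* at alpha .01 produces a cut-off for McFadden ΔR², "which returns an effect size that would be unlikely given the null hypothesis of no DIF", with a floor of .001. Then: "Within each scale, we will select the smallest McFadden R^2 across all of the items". That one value is applied to every item in the scale. The criterion is raised, in steps of .005, only if more than half of the items are flagged.

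The SAP gives no number of flagged items, scales or strata that would count for or against the hypothesis, no expected number of chance flags, and no adjustment across items, scales or strata.

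**The concern.** A cut-off set at .01 for one item says how unusual one flag is. It does not say how unusual a list of flags is when roughly a hundred items are tested in each of four strata. If finding some flags counts as support, data with no literacy bias will often appear to support the hypothesis. At stake is the claim drawn from it: that these questionnaires are biased by literacy on paper and that their items need work.

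**Working it through.** **The plan's own figure.** 1216 / (2 languages × 2 formats) = 304, which matches the stated stratum size. It is the original design; the final N of 728 gives a mean of 728/4 = 182. The false-flag rates below do not change with this, because the simulated cut-off is set for the N in hand.

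**Item count.**

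| Scale | Items | SAP source |
|---|---|---|
| PROMIS Profile, seven DIF scales | 56 | 57-item Profile (sleep mediation section), less one pain-intensity item |
| PTSD Checklist | 20 | Health questionnaires |
| RRS | 10 | Prediction of depression |
| PHQ-9 | 9 | Prediction of depression |
| Meaning and Purpose | 8 | Meaning and Purpose Analyses |
| Total | 103 | 11 scales |

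Two assumptions enter: pain intensity, which is not in the DIF list, is one item; and the other 56 split evenly, 56/7 = 8 per PROMIS scale. The Berlin length is not stated, so it is left out. The separate RRS subscale runs are also left out, and each item is counted once although uniform, non-uniform and total DIF are all listed. These omissions understate the number of tests.

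**At least one false flag, rate .01, items independent:** 1 − .99^m.

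| Strata | m | Expected false flags | P(at least one) |
|---|---|---|---|
| One | 103 | 1.03 | 64.5% |
| Two paper | 206 | 2.06 | 87.4% |
| All four | 412 | 4.12 | 98.4% |

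Allowing up to 10 Berlin items and 10 further RRS subscale tests (123 per stratum) gives 91.6% on paper and 99.3% over four strata.

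**Two or more scales flagged on paper.** A scale of k items is flagged with probability p = 1 − .99^k: .0773 for 8 items (eight scales), .0865 for 9, .0956 for 10, .1821 for 20.

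- One language: P(none) = .99^103 = .3552. P(exactly one) = .3552 × Σ p/(1 − p) = .3552 × 1.093 = .388. P(two or more) = 1 − .3552 − .3881 = 25.7%.
- Both languages, counting distinct scales (k replaced by 2k): P(none) = .1261, P(exactly one) = .2916, P(two or more) = 58.2%.

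**Smallest cut-off applied to all items.** This can only raise the per-item rate above .01; by how much depends on the items. In a simulated no-DIF scale (eight items, five categories, a trait difference between groups, 700 data sets at each of N = 304 and N = 182), the rate was about 2%. At an illustrative .02:

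- Any flag on paper: 1 − .98^206 = 98.4%.
- Two or more scales on paper: 1 − .1248 − .2901 = 58.5% in one language; 1 − .0156 − .0815 = 90.3% over both.

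**Independence within a scale.** In the same simulation, with each item at its own cut-off, at least one of eight items was flagged in 7.9% (N = 304) and 7.6% (N = 182) of data sets, against 1 − .99^8 = 7.7%. The assumption looks adequate there. The simulated cut-offs were about .009 and .015, so the .001 floor did not bind.

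**The case against.** The plan does calibrate its flags: the simulated cut-off is a null benchmark for each item, and .01 is stricter than the general .05. A reader might infer that the plan has no null benchmark at all. That is wrong; what is missing is a benchmark for the count.

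A reader might also take 98% as the chance that the primary hypothesis is confirmed by noise. That figure uses the weakest reading, one flag anywhere in four strata. The other predictions are more demanding under no DIF at .01:

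- Multiple scales on paper in both languages combined still fails about 42% of the time (100 − 58).
- A flag in every stratum has probability .645^4 = 17%.
- With paper and touchscreen counts as independent Binomial(206, .01), paper exceeds touchscreen about 40% of the time, and about 29% with at least one touchscreen flag.

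Lower slopes with low literacy are predicted too. So the documents do not support saying that the set of hypotheses can hardly fail.

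Nor does one stray flag lead to rewriting items: the SAP ties that inference to multiple scales. It also reports ΔR², item parameters by group, θ against DIF-purified θ, and test characteristic curves, all of which help show whether a flag matters.

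These points narrow the concern but do not remove it. The touchscreen comparisons have no test or margin, the impact measures carry no decision rule, and about one chance flag in 103 items comes nowhere near the 50% trigger.

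**Conclusion.** The concern holds in this form: there is an item-level null threshold but no study-level criterion. Under no DIF, the paper-based hypothesis, read as any flag, would be met about 87% of the time at .01, and the multiple-scales version about 26% (one language) or 58% (both). At an illustrative 2% per item these become about 98%, 59% and 90%.

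The figures rest on the 103-item sum with its two assumptions, independence between items and scales, and one test per item. The 2% comes from assumed item parameters, not from the documents. Flagged items remain usable as description. What cannot be claimed, as the SAP stands, is that finding some of them confirms the hypothesis.

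**What to change.** Add a study-level rule to the SAP.

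1. In each no-DIF data set from the planned *lordif* simulations, apply the actual flagging rule, including the smallest cut-off and the .001 floor, and count flagged items per scale.
2. Combine counts across scales within a stratum. The simulations are planned scale by scale and do not give a joint null, so either convolve the per-scale counts with independence across scales stated as an assumption, or simulate the scales jointly. Different strata contain different people and can be combined directly.
3. Declare the paper-based and multiple-scales hypotheses supported only if the observed number of flagged items, or of flagged scales, exceeds the 95th percentile of its null distribution.
4. Print the expected number of false flags beside each list of flagged items.

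For scale: with independent items, the paper strata would need at least 6 flags of 206 at a rate of .01 (binomial tail 1.8%), but at least 9 at .02 (2.4%). This is why the count should come from the rule actually used.

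The cost is SAP wording, a little more simulation work, and a hypothesis that becomes harder to confirm. No new data are needed.
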